4. SELECTION AND WITHDRAWAL OF SUBJECTS

Subjects must fulfill all the inclusion and exclusion criteria and the investigator must obtain written approval from the Medical Monitor, to confirm any deviation from these *prior to* randomization of the subject.

4.1 Inclusion Criteria

- 1. 18 years of age or older.
- 2. Diagnosis of bilateral primary open angle glaucoma or ocular hypertension.
- 3. One qualifying IOP criteria after washout:
 - Baseline (Day 1) at T_0 ($T_0 = 8$ am ± 30 min [IOP time]) IOP ≥ 23 mmHg in the study eye.
- 4. IOP criteria after washout \leq 32 mmHg OU at all qualifying time points/visits.
- 5. Best-corrected visual acuity (BCVA) in both eyes of 20/200 or better on Snellen, equivalent to + 1.0 log Mar at Visit 1 Screening.
- 6. Able and willing to sign informed consent, follow study instructions and complete all study visits.
- 7. As applicable, must be willing to discontinue the use of all ocular hypotensive medication(s) in both eyes prior to receiving the study medication and for the entire course of the study.
- 8. Able to self-administer or have a caretaker administer investigational product eye drops.

4.2 Exclusion Criteria

Exclusion criteria:

Investigators will exclude any subject who they consider unsafe for participation in this study or unlikely to complete the requirement of the protocol for any reason.

Ocular:

Exclude subjects with:

- Closed or very narrow angles (Grade 0-1) (see Section 5, gonioscopy) or those the investigator judges as occludable and/or with evidence of peripheral anterior synechiae (PAS) ≥ 180 degrees by gonioscopy within 6 months prior to Screening Visit in either eye. (Patent laser iridotomy with Grade 1-2 angles is acceptable in either eye, providing the PAS criteria are still met).
- 2. Previous glaucoma intraocular surgery in either eye(including cyclodestructive procedures). Prior laser trabeculoplasty (ALT or SLT) in either eye is allowed if performed more than 6 months prior to Screening Visit.
- 3. Any non-glaucoma intraocular surgery within 3 months prior to Screening Visit in either eye.
- 4. Intraocular laser surgery such as laser capsulotomy, laser iridotomy, and/or retinal laser within 1 month prior to Screening Visit in either eye.
- 5. Significant media opacity in either eye that would impede adequate posterior segment examination.
- 6. Contraindications to pupil dilation in either eye.
- 7. Other forms of glaucoma such as primary congenital, juvenile onset, chronic angle closure, and secondary glaucoma of any type including corticosteroid-induced, inflammation-induced, or exfoliation glaucoma in either eye. Pigment dispersion syndrome/glaucoma is permitted in either or both eyes.
- 8. Clinically significant corneal dystrophy, epithelial or endothelial disease, corneal irregularities or scarring that, in the investigator's judgment, would impede an accurate measurement of IOP or visualization of intraocular anatomy in the study eye.
- 9. Prior netarsudil use in either eye which resulted in clinically significant adverse events leading to discontinuation of treatment including: conjunctival hyperemia, subconjunctival hemorrhage, cornea verticillata, or reticular bullous epithelial edema.
- 10. History of refractive surgery in either eye (i.e., radial keratotomy, PRK, LASIK).
- 11. History of corneal cross-linking procedure in either eye.
- 12. Unwillingness to be contact lens free during study participation.
- 13. Any history of uveitis, keratitis, or scleritis in either eye. Note: SPK associated with ocular surface disease is permitted.
- 14. Any history of penetrating ocular trauma in either eye.
- 15. History within 3 months prior to Screening Visit of clinically significant moderate or severe chronic or active blepharitis, ocular dermatitis, or recent ocular conjunctivitis and/or ocular inflammation in either eye. Mild blepharitis, hyperemia (due to prostaglandin use) and/or blepharitis, and/or mild or inactive seasonal allergic conjunctivitis and non-infectious dermatitis are acceptable.
- 16. Corneal thickness < 480 or > 620 μm in the study eye. Pachymetry measurement within 6 months prior to Screening Visit is acceptable.
- 17. Advanced or severe glaucoma with progressive visual field loss, NFL thinning documented by OCT, and/or optic nerve changes in either eye that, in the investigator's best judgment,

prevent safe withdrawal from treatment for the time periods required in this protocol. Notes: 1) Subjects may be switched to a different IOP lowering therapy with a shorter washout period as long as the appropriate washout is met prior to Visit 2. 2) Visual fields must be reliable, defined as those with a) fixation losses less than or equal to 33%, b) false positives less than or equal to 33% and c) false negatives less than or equal to 33%.

- 18. In the investigator's best judgment, progressive retinal (including, but not limited to worsening dry AMD, presence of active wet AMD, or unstable diabetic retinopathy) or optic nerve disease in either eye from any cause other than glaucoma. Mild BDR is permitted.
- 19. Any prior intravitreal corticosteroid injection in either eye.
- 20. Sub-tenon's, sub-conjunctival or periocular corticosteroid injections within the 6 months prior to Screening Visit in either eye.
- 21. Any use of ocular topical corticosteroids in either eye within 7 days, or chronic (as determined by the investigator) topical steroids within 28 days, prior to Baseline Day 1 and ensuing trial participation.
- 22. Known hypersensitivity to any component of the H-1337 formulation, including BAK, timolol maleate, or to topical anesthetics or diagnostic drops to be used during the study.
- 23. Any ocular condition that, in the investigator's judgment, could prevent the subject from safe participation the study.
- 24. Planned ocular surgery or intraocular injection procedure in either eye during study participation.

General/Systemic:

Exclude subjects with:

- 25. Participation in a clinical study with use of any investigational drug or treatment within 30 days prior to Baseline (Day 1).
- 26. Prior use of H-1337.
- 27. Clinically significant systemic, psychiatric or psychological disease (for example, renal, hepatic, uncontrolled diabetes, uncontrolled blood pressure, autoimmune disorders, psychiatric disorders, endocrine disorders, or any other disorders) or dependency which, in the investigator's judgment, would be unsafe and interfere with interpretation of the study results or the subject's ability to comply with the study requirements.
- 28. Contraindication to beta-blocker usage including: reactive airway disease, uncontrolled heart failure, or second as well as third degree cardiac block, myasthenia gravis.
- 29. Anticipated changes or initiation of medications which might affect IOP and/or systemic blood pressure within 7 days prior to Baseline/Day 1 (e.g., including, but not limited to: oral anti-hypertensives such as sympathomimetic agents, beta-adrenergic blocking agents, alpha agonists, alpha adrenergic blocking agents, calcium channel blockers, angiotensin converting enzyme inhibitors [diuretics are allowed]), and 2 months prior to Baseline/Day 1 for corticosteroids (i.e., oral, nasal, topical [dermal, mucosal], and/or inhaled corticosteroids). If there are no further anticipated changes in medications that could affect IOP and/or systemic blood pressure, then once the subject is stable on their new dose of medication for the required time period, the subject may complete the Baseline Visit, assuming that all other screening requirements are met. Medications used on an adjustable or sliding scale based on testing results are allowed. Note: Vaccines are permitted.
- 30. Women of childbearing potential who are pregnant, nursing, planning a pregnancy, or not using a medically acceptable form of birth control. An adult woman is considered to be of

childbearing potential unless she is one year post-menopausal or three months post-surgical sterilization. All females of childbearing potential must have a negative urine pregnancy test result at the Screening Visit and at Baseline (Day 1) prior to randomization in the study and must not intend to become pregnant during the study.

- 31. History of drug or alcohol abuse within the last 5 years.
- 32. Unwillingness to refrain from consumption of alcohol or cannabinoids, including tetrahydrocannabinol (THC) and cannabidiol (CBD), in any form by any delivery route, on the day prior to each study visit after Visit 1 Screening.
- 33. Related to site study staff and/or site employees.

4.3 Subject Withdrawal and/or Discontinuation

Subjects are free to discontinue their participation in the study at any time without prejudice to further treatment. The investigator must withdraw any subject from the study at their request. Subjects should provide the reason for withdrawal and confirm whether they are withdrawing consent or withdrawing from IP treatment. The investigator or D. Western Therapeutics, Inc. designee, may withdraw the subject from IP treatment for any reason or if the subject meets any of the following criteria.

- Experiences a serious or intolerable AE that is judged by the investigator to preclude further study participation.
- Develops a clinically significant laboratory or other abnormality that is judged by the investigator to be potentially related to IP.
- Requires a medication that is prohibited by the protocol. Contact the Medical Monitor to discuss exiting a subject due to use of a prohibited medication before exiting the subject.
- Does not follow the protocol procedures, including noncompliance.
- Is lost to follow-up; every effort should be made to contact the subject.
- Administrative reasons, including termination of the trial by the Sponsor, unavailable for follow-up procedures.
- Experiences glaucomatous progression and/or unacceptable IOP elevation, per the discretion of the investigator.

Should a subject's medical or mental condition change or become unstable during the study, such that the ability of the subject to continue in this study becomes compromised or, in the investigator's judgment, their health is jeopardized, or further continuation is unadvisable, the subject may be withdrawn from study treatment.

If a subject withdraws or is withdrawn from IP treatment, every effort should be made to ensure the subject continues to participate in the remaining trial visits.

If a subject withdraws or is withdrawn from IP treatment, either at her/his request or at the discretion of the investigator or D. Western Therapeutics, Inc. the reason for withdrawal should be recorded. All subjects withdrawing or withdrawn from IP dosing, regardless of cause, will return within 14 days from their last dose of IP to complete Early Termination visit assessments; consult the Medical Monitor to determine which diurnal measurements, if any, are required for the ET visit.

Version Date: 19 Jan 2024

It is vital to obtain follow-up data for any subject withdrawn due to an AE. In any case, every effort must be made to undertake safety follow-up procedures.

If a subject does not return for a scheduled visit, every effort should be made to contact the subject. If every effort is made to contact the subject (including two telephone calls and a traceable letter sent to the subject) and these attempts are unsuccessful, the subject is considered lost to follow-up.

4.4 Medication

During the washout period between Visits 1 and 2 from prior IOP-lowering therapy, topical carbonic anhydrase inhibitors (CAI) (i.e., Dorzolamide (Trusopt®) or Brinzolamide (Azopt®) will be permitted, but will not be provided by the Sponsor. Should a topical CAI be employed during the washout period, the applicable washout for CAIs should be implemented and the CAI should be discontinued 5 days prior to Baseline (Day 1).

Current systemic mediations which may influence intraocular pressure should be stable without anticipated changes over the course of the trial. Should a subject's medical condition change or become unstable during the study, such that the change in non-ocular medication that can or may affect IOP are added or altered (i.e., steroids, systemic beta blockers, etc.), the subject's condition should be reviewed with the study Medical Monitor. If the subject is withdrawn from IP treatment, the subject will continue to be followed during routine trial visits or until he/she returns within 14 days from the last dose of IP to complete the Early Termination visit.

If, during the study, an investigator determines the IOP is inadequately controlled such that the safety of the subject is compromised, the PI may withdraw the subject from IP treatment and institute IOP treatment.

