- 9. Prior netarsudil use in either eye which resulted in clinically significant adverse events leading to discontinuation of treatment including: conjunctival hyperemia, subconjunctival hemorrhage, cornea verticillata, or reticular bullous epithelial edema.
- 10. History of refractive surgery in either eye (i.e., radial keratotomy, PRK, LASIK).
- 11. History of corneal cross-linking procedure in either eye.
- 12. Unwillingness to be contact lens free during study participation.
- 13. Any history of uveitis, keratitis, or scleritis in either eye. Note: SPK associated with ocular surface disease is

permitted.

- 14. Any history of penetrating ocular trauma in either eye.
- 15. History within 3 months prior to Screening Visit of clinically significant moderate or severe chronic or active blepharitis, ocular dermatitis, or recent ocular conjunctivitis and/or ocular inflammation in either eye. Mild blepharitis, hyperemia (due to prostaglandin use) and/or blepharitis, and/or mild or inactive seasonal allergic conjunctivitis and non-infectious dermatitis are acceptable.
- 16. Corneal thickness < 480 or > 620 μm in the study eye. Pachymetry measurement within 6 months prior to Screening Visit is acceptable.
- 17. Advanced or severe glaucoma with progressive visual field loss, NFL thinning documented by OCT, and/or optic nerve changes in either eye that, in the investigator's best judgment, prevent safe withdrawal from treatment for the time periods required in this protocol. Note: 1) Subjects may be switched to different IOP lowering therapy with a shorter washout period as long as the appropriate washout is met prior to Visit 2. 2) Visual fields must be reliable, defined as those with a) fixation losses less than or equal to 33%, b) false positives less than or equal to 33% and c) false negatives less than or equal to 33%.
- 18. In the investigator's best judgment, progressive retinal (including, but not limited to worsening dry AMD, presence of active wet AMD, or unstable diabetic retinopathy) or optic nerve disease in either eye from any cause other than glaucoma. Mild BDR is permitted.
- 19. Any prior intravitreal corticosteroid injection in either eye.
- 20. Sub-tenon's, sub-conjunctival or periocular corticosteroid injections within the 6 months prior to Screening Visit in either eye.

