3.5 Duration

Each subject's participation will consist of two phases: a Screening Phase (Screening and Baseline Visit 2 and Visit 3 Pre-T₀) where subjects will suspend dosing of any current ocular hypotensive therapy, and a Dosing Phase, starting on Day 1 after Pre-T₀. If a subject is not using ocular hypotensive therapy at Screening Visit 1, there is no applicable washout period and the Baseline Visit should occur within 1 to 42 days after Screening Visit 1.

A subject could participate in the study for a total of up to approximately 11 weeks. Subjects who meet the applicable inclusion/exclusion criteria at the Screening Visit will discontinue use of any current ocular hypotensive therapy during the washout period. (Note: At Investigator's discretion for subject's safety, initiation of a different IOP lowering therapy with a shorter washout period is permitted during a long washout period provided all appropriate washout periods are met prior to Visit 2.) The washout duration will be dependent on the subject's prestudy ocular hypotensive therapy. The table below lists the applicable washout durations for various pre-study ocular hypotensive medications. (Note: This table may not be inclusive of all

ocular hypotensive medications. The Medical Monitor should be contacted for further information regarding the washout period of an ocular hypotensive not included in the table.) If the Investigator assesses an acceptable risk, subjects may extend washout up to 49 days to accommodate scheduling.

 Table 2:
 Ocular Hypotensive Medication Washout Schedule

Ocular Hypotensive Generic/Trade Names	Washout period* (between Screening and Baseline Visit)
Muscarinic agonists (e.g., pilocarpine) and Oral or Topical Carbonic Anhydrase Inhibitors (CAI)	≥ 5 days
Beta-adrenoceptor antagonists	≥ 6 weeks
Alpha adrenoceptor agonists	≥ 5 weeks
Prostaglandin analogues, Combination Drugs (use longest wash-out period of individual components) *	≥6 weeks
Rho-associated protein kinase (ROCK) inhibitors	≥ 6 weeks

^{*}The washout period of longest duration should be used when the subject is taking multiple ocular hypotensive medications from more than one class. Additional +1 week extended washout permitted to accommodate scheduling considerations (Stroman et al., 1997; Johnson and Jampel, 2021).

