Following the applicable washout period, the subject will return for applicable inclusion/exclusion evaluations on the Baseline Visit (Day 1) and a subject meeting all inclusion/exclusion criteria at $Pre-T_0$ will be randomized to IP. Both eyes will be dosed and evaluated for safety throughout the trial. The study eye is the eye that meets all entry criteria including the IOP criteria after washout. Should both eyes meet the criteria then the study eye will be defined as the eye with the higher $Pre-T_0$ 8 am IOP on Baseline (Day 1). If both eyes have the same $Pre-T_0$ 8 am IOP on Baseline (Day 1), the study eye will be the right eye.

Dosing will be initiated on Day 1 in the office after measurement of the $Pre-T_0 \ 8$ a.m. IOP and the completion of all examinations required prior to the $Pre-T_0 \ 8$ a.m. IOP measurement. The subject will be dosed for up to 28 days during which time they will be monitored for safety, tolerability, and efficacy assessments according to the Schedule of Study Assessments and Procedures.

The duration of participation for subjects in each stage will be as follows:

Screening Visit: 1 day

Washout Period: up to 42 days (+ 7 days) depending on pre-study ocular hypotensive therapy

Treatment Period: 28 days \pm 2 days

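### Section 4.4 counts the stop of a bridging CAI back from Day 1, so Day 0 baseline IOP can follow only 1 to 4 drug-free days instead of 5

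*Protocol*

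**What the plan says.** Protocol Section 4.4 allows a topical CAI as a bridge "During the washout period between Visits 1 and 2 from prior IOP-lowering therapy". It asks that the CAI washout be applied, then gives the date: "the CAI should be discontinued 5 days prior to Baseline (Day 1").

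Two other places use an earlier endpoint. Section 3.5 allows a substitute IOP-lowering drug during a long washout "provided all appropriate washout periods are met prior to Visit 2". Exclusion criterion 17 (synopsis and Section 4.2) allows the switch "as long as the appropriate washout is met prior to Visit 2".

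Table 2 in Section 3.5 sets at least 5 days for CAIs and muscarinic agonists, counted "between Screening and Baseline Visit". The text after the table points to Day 1: "Following the applicable washout period, the subject will return for applicable inclusion/exclusion evaluations on the Baseline Visit (Day 1"). Earlier in the same section, however, the screening phase is described as "Screening and Baseline Visit 2 and Visit 3" Pre-T0, so the term is not used in one sense only.

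Table 1 places Visit 2 (Day 0) 4 to 1 days before Day 1. SAP Section 4.1 takes the IOP baseline at Pre-T0 from Day 1. It takes the baselines at +2, +4, +8 and +12 h, and the mean diurnal baseline, from Day 0.

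**The concern.** The IOP curve that serves as baseline for almost every primary time point is recorded at Visit 2, but the Section 4.4 stop date protects only Visit 3. Two groups can reach Visit 2 short of the protocol's own 5-day minimum:

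- subjects bridged with a CAI, at a site that schedules from the 4.4 sentence;
- subjects whose only pre-study drug is a CAI or muscarinic agonist, washed out for the Table 2 minimum counted to Day 1. The before-Visit-2 notes address only subjects switched to another therapy, so they do not protect this group.

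If some drug effect remains at Visit 2, the Day 0 readings are too low and change from baseline is understated at the post-dose hours and for mean diurnal IOP. That applies to timolol as well. No arm receives vehicle alone, so timolol's own change is the main internal check that the control performed. The Pre-T0 baseline, taken on Day 1, would also have a longer washout than the later-hour baselines. Eligibility would not catch a suppressed Day 0 reading: the 23 mmHg minimum in Section 4.1 applies only at T0 on Day 1.

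**Working it through.** The plan states no figure to reproduce here. The check is date arithmetic and a count of time points.

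**Inputs**
- CAI stop: 5 days before Day 1 (Protocol 4.4).
- Minimum washout: 5 days for CAIs and muscarinic agonists, 5 weeks for alpha agonists, 6 weeks for beta-blockers, prostaglandins and ROCK inhibitors (Table 2).
- Visit 2: 1 to 4 days before Day 1 (Table 1).
- Primary time points: 5 on Day 28 and 4 on Day 1 in SAP 4.3; 4 on Day 28 and 3 on Day 1 in Protocol 8.4, which leaves out +12 h.
- Baseline source: Day 1 for Pre-T0, Day 0 for all later hours (SAP 4.1).

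**Step 1. Drug-free days at Visit 2** = 5 − (days from Visit 2 to Day 1)

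| Visit 2 before Day 1 | Drug-free days at Visit 2 | Shortfall against 5 days |
|---|---|---|
| 1 day | 5 − 1 = 4 | 1/5 = 20% |
| 2 days | 5 − 2 = 3 | 2/5 = 40% |
| 3 days | 5 − 3 = 2 | 3/5 = 60% |
| 4 days | 5 − 4 = 1 | 4/5 = 80% |

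No permitted Visit 2 date reaches 5 days.

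**Step 2. Does this matter for the longer washouts?** The same 1 to 4 days are lost, but from 35 or 42 days: 1/35 to 4/35 = 2.9% to 11.4%, and 1/42 to 4/42 = 2.4% to 9.5%. In practice the point concerns the 5-day class only.

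**Step 3. How many primary time points use a Day 0 baseline?** The only primary time point with a Day 1 baseline is Day 28 Pre-T0.
- SAP: 4 on Day 1 + (5 − 1) on Day 28 = 8 of 9.
- Protocol list with the same time-matching: 3 on Day 1 + (4 − 1) on Day 28 = 6 of 7.

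**Step 4. Size in mmHg.** This needs the share of subjects affected and the IOP effect remaining 1 to 4 days after the last dose. The documents give neither, so no estimate is made.

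**The case against.** The strongest reply is that bridged subjects are already covered. Section 3.5 makes completed washout before Visit 2 a condition of bridging, criterion 17 repeats it, and Section 4.4 itself opens by placing washout between Visits 1 and 2. A site that obeys the stricter text has no short washout. This stands as a limit on how often the problem arises. It does not remove the conflict, because the sentence that gives the CAI stop date is the looser one.

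For subjects on a CAI or muscarinic agonist alone, the Table 2 endpoint is open to argument. Visit 2 is a tenable reading, though Day 1 is the more natural one. Five days is also a minimum, and any drug from another class triggers a longer washout, so the group may be small or empty.

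A reader might infer that the SAP departs from the protocol's baseline without declaring it. The documents do not support that. Protocol 6.1 defines change at matched time points, and the Day 1 readings from +2 h onward are taken after dosing. A matched reading before first dose at those hours can come only from Day 0, so SAP 4.1 makes explicit what the protocol implies. The SAP baseline is sound; the washout rule needs to match it.

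**Conclusion.** The point holds as a conflict between instructions. Followed literally, the Section 4.4 date gives 1 to 4 drug-free days instead of 5 at the readings that serve as baseline for 8 of the SAP's 9 primary time points. For subjects on a CAI or muscarinic agonist alone, it also depends on reading Table 2's endpoint as Day 1.

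A reader might go further and infer that the non-inferiority comparison is biased. That is not supported. Washout comes before randomization, so short washouts should fall evenly across arms, and the primary model compares arms with adjustment for baseline. What remains is possible slight understatement of within-arm change and slightly noisier baselines. Both assume some drug effect persists at Visit 2, which the documents do not show. The effect cannot be sized from the documents and is probably small. The case for correction rests on a cheap fix and on how many primary time points use Day 0.

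**What to change.** In Protocol Section 4.4, require the bridging CAI to be stopped at least 5 days before Visit 2 (Day 0). In Table 2, state for the 5-day class (CAIs and muscarinic agonists) that washout must be complete before Visit 2. The longer classes need no change.

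The stop then falls 5 + 1 = 6 to 5 + 4 = 9 days before Day 1, and every Day 0 baseline follows at least 5 drug-free days. This stays inside the slack in the Table 2 footnote, "Additional +1 week extended washout permitted to accommodate scheduling considerations", which gives 5 + 7 = 12 days. The cost is 1 to 4 more days off therapy for the subjects concerned, slightly tighter scheduling, and a minor protocol amendment that needs IRB approval before use (Section 12.2).
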